## Protocol Synopsis

**Title:** A Phase 1a/1b Study of Cabiralizumab in Combination with Nivolumab in Patients with Selected Advanced Cancers

**Protocol Number:** FPA008-003

**Clinical Phase:** 1a/1b

**Sponsor:** Five Prime Therapeutics, Inc.

**Study Centers:** There will be approximately 50 study centers participating in this study.

### Objectives:

#### Phase 1a Objectives

- Primary
- To assess the safety and tolerability of cabiralizumab as monotherapy
  - To assess the safety and tolerability of cabiralizumab in combination with nivolumab
  - To determine the recommended dose (RD) of cabiralizumab in combination with a fixed dose of nivolumab
- Secondary
- To characterize the PK profile of cabiralizumab
  - To characterize the PK profile of nivolumab when administered in combination with cabiralizumab
  - To characterize the immunogenicity of cabiralizumab and nivolumab
  - To characterize the PD profile of cabiralizumab and nivolumab by analyses of biopsies (including IHC analyses of CD8, CD68, and other selected biomarkers)

#### Phase 1b Objectives

- Primary
- To evaluate the clinical benefit of cabiralizumab in combination with nivolumab in patients with selected advanced cancers through the analysis of objective response rate (ORR)
  - To evaluate the safety and tolerability of cabiralizumab in combination with nivolumab in patients with selected advanced cancers treated at the RD

## Phase 1b Objectives (Cont.)

### Secondary

- To evaluate the clinical benefit of cabiralizumab in combination with nivolumab in patients with selected advanced cancers through the analysis of overall survival (OS), duration of response (DOR), and progression free survival (PFS)
- To characterize the PK profile of cabiralizumab when administered in combination with nivolumab
- To characterize the PK profile of nivolumab when administered in combination with cabiralizumab
- To characterize the immunogenicity of cabiralizumab and nivolumab
- To characterize the PD profile of cabiralizumab and nivolumab by analyses of biopsies (including IHC analyses of CD8, CD68, and other selected biomarkers)
- To assess the association of selected biomarker measures and clinical efficacy measures using pre-treatment and on-treatment tumor biopsies

### Investigational Products

Cabiralizumab Solution for Intravenous Infusion  
Nivolumab Solution for Intravenous Infusion

### Study Design

This study is a Phase 1a and 1b, open-label, multicenter, dose escalation and dose expansion study to evaluate the efficacy, safety, tolerability, PK, and PD of cabiralizumab as monotherapy and in combination with nivolumab in patients with selected advanced cancers. Cabiralizumab is a humanized monoclonal antibody directed against CSF1R and nivolumab is a fully human monoclonal antibody directed against PD-1. For the combination arms of the study (except for the 3-week dosing regimen cohort -Cohort 1aD), cabiralizumab and nivolumab will be given on Day 1 of each 14-day treatment cycle. For cohort 1aD, cabiralizumab and nivolumab will be administered on Day 1 of each 21-day treatment cycle. Nivolumab will be administered as an IV infusion over 30 minutes followed by a 30- to 60-minute rest, and then cabiralizumab will be administered as an IV infusion over 30 minutes.

The study includes Phase 1a and Phase 1b. Patients will be enrolled into either Phase 1a or Phase 1b of the study.

Phase 1a consists of 7 dose escalation cohorts, one 3-week dosing regimen cohort. Phase 1a may also include up to 40 additional patients that will be enrolled for further exploration of safety and PK.

Phase 1b consists of 7 tumor-specific expansion cohorts across 6 cancer types.

## Study Design (Cont.)

### Phase 1a: Dose Escalation

In Phase 1a, a modified 3 + 3 + 3 design will be used to assess the safety of cabiralizumab in monotherapy and in combination with nivolumab.

Dose escalation will be based on the number of DLTs experienced during the DLT evaluation interval as determined by the Investigators and Medical Monitor (see Section 3.1.2.1.1 for DLT criteria). The DLT evaluation interval begins on the first day of treatment and continues for 28 days. Patients who receive at least 2 doses of study drug during the 28-day evaluation interval or patients who discontinue study treatment for drug-related AEs before receiving 2 doses of study drug will be considered evaluable for DLT determination. In consultation with Investigators, the Sponsor has the option to investigate dose levels different than those defined in the protocol.

Dose escalation in Phase 1a proceeds as follows:

- If none of the first 3 evaluable patients in a dose cohort experiences a DLT within the DLT evaluation interval, then the next 3 patients will be treated at the next higher dose cohort.
- If 1 of the first 3 evaluable patients in a cohort experiences a DLT within the DLT evaluation interval, then 3 additional patients will be treated in that dose cohort.
  - If no more than 1 of the first 6 evaluable patients experiences a DLT during the DLT evaluation interval, then the next 3 patients will be enrolled at the next higher dose cohort.
  - If 2 of the first 6 evaluable patients in a cohort experience a DLT, that cohort will be expanded to 9 evaluable patients.
- If 2 of the first 3 evaluable patients experience a DLT within the DLT evaluation interval, then 6 additional patients may be treated in that dose cohort, upon approval of Investigators and the Medical Monitor.
- If the incidence of DLT is > 33% in the overall population up to 9 patients, that dose level has exceeded the MTD and dose escalation will be terminated.

**Study Design  
(cont.)**

Phase 1a: Dose  
Escalation

[REDACTED]	
[REDACTED]	[REDACTED]
[REDACTED]	[REDACTED]
[REDACTED]	[REDACTED]
[REDACTED]	[REDACTED]
[REDACTED]	[REDACTED]
[REDACTED]	[REDACTED]
[REDACTED]	[REDACTED]
[REDACTED]	[REDACTED]
[REDACTED]	[REDACTED]
[REDACTED]	[REDACTED]
[REDACTED]	[REDACTED]
[REDACTED]	[REDACTED]

The study will consist of 3 periods including screening (up to 28 days), treatment, and follow-up.

The DLT period is defined as the first 28-days (completion of 2 cycles). Upon the first occurrence of a delayed DLT (defined as any DLT that occurs between 4 to 6 weeks after administration of study drug) in any patient enrolled in Phase 1a dose escalation, all ongoing and subsequent DLT periods will be expanded to 42 days for all remaining and subsequent patients enrolled in Phase 1a dose escalation. If no patient experiences a delayed DLT, the DLT period will remain at 28 days for all patients. AST, CK, or LDH laboratory abnormalities without clinical sequelae are not considered a delayed DLT (see Section 3.1.2.1.1).

In the event that no MTD is identified and drug exposure exceeds those deemed necessary based on nonclinical pharmacology data or the clinical PK and PD data (if available), FivePrime and the Investigators may make a decision to discontinue dose escalation.

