Depending on the outcome of the cohorts described above, alternative dose cohorts may be opened. All dose escalation decisions will be based on assessment of DLTs, overall safety, and tolerability. Dose escalation decisions will be agreed upon between the Investigators and Sponsor. Prior to initiating each new dose level or expanding an existing dose level, a safety teleconference will be held wherein the Investigators and Sponsor will review patient data, including but not limited to demographics, dosing, concomitant medications, hematology, serum chemistry, and AEs; and confer and document agreement that dose escalation or expanding an existing dose level is considered appropriate. If the Investigators and Sponsor collectively agree, following review of safety, PK, and PD data (if available), that a different dose escalation scheme (e.g., an alternative dose of cabiralizumab monotherapy or in combination with nivolumab) should be used than the one outlined, this will be permitted. Review of safety, PK, and PD profiles may inform decisions to add cohorts with alternative dose levels or dose regimens (e.g., less frequent dosing) in order to reach an optimal target exposure.

Dose escalation will be based on the number of DLTs experienced during the DLT evaluation interval as determined by the Medical Monitor and Investigators (see Section 3.1.2.1.1 for DLT criteria). The DLT evaluation interval begins on the first day of treatment and continues for 28 days. Patients that receive at least 2 doses of study drug during the 28-day evaluation interval or patients who discontinue study treatment for drug-related AEs before receiving 2 doses of study drug will be considered evaluable for DLT determination. In consultation with Investigators, the Sponsor has the option to investigate alternative dose levels to those defined in the protocol.

Dose escalation in Phase 1a will proceed as follows:

- If none of the first 3 evaluable patients in a dose cohort experiences a DLT within the DLT evaluation interval, then the next 3 patients will be treated at the next higher dose cohort.
- If 1 of the first 3 evaluable patients in a cohort experiences a DLT within the DLT evaluation interval, then 3 additional patients will be treated in that dose cohort.
  - If no more than 1 of the first 6 evaluable patients experiences a DLT during the DLT evaluation interval, then the next 3 patients will be enrolled at the next higher dose cohort.

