#### **3.1.2.1.1 Dose Limiting Toxicity**

A DLT is defined as a study drug-related  $\geq$  Grade 3 AE (using National Cancer Institute [NCI] Common Terminology Criteria for Adverse Events [CTCAE] v 4.03) occurring during the first 28-days, excluding: Grade 3 tumor flare (defined as local pain, irritation, or rash localized at sites of known or suspected tumor), Grade 3 rash, Grade 3 immune-related adverse event (irAE) that resolved to a Grade 1 or less within 14 days, or a transient (resolving within 6 hours of onset) Grade 3 infusion-related AE. Any recurrence of Grade 3 rash, Grade 3 immune-related AE, or Grade 3 infusion-related AE will be considered a DLT. An irAE is defined as a clinically significant AE that is associated with study drug exposure, of unknown etiology, and is consistent with an immune-mediated mechanism.

In the absence of clinical symptoms and other accompanying changes in bilirubin or ALT (as noted in appendices F, G, and H), serum elevations of AST/ALT  $> 12$  xULN and  $\leq 20$  xULN that last for  $< 7$  days will not be considered a DLT and serum elevations of CK and/or LDH  $> 15$  xULN and  $\leq 20$  xULN that last for  $< 7$  days will not be considered a DLT.

Upon the first occurrence of a delayed DLT in any patient enrolled in Phase 1a (defined as any DLT that occurs between 4 to 6 weeks after administration of study drug), all ongoing and subsequent DLT periods will be expanded to 42 days for all remaining and subsequent patients enrolled in Phase 1a dose escalation. If no patient experiences a delayed DLT, the DLT window will remain at 28 days for all patients.

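### The synopsis exempts AST, CK and LDH abnormalities from the delayed-DLT trigger without the limits in Section 3.1.2.1.1, and the 28-day DLT wording and evaluability rule were not adapted to a 42-day period

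*Protocol*

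**What the plan says.** **Extension.** The Protocol Synopsis (Phase 1a: Dose Escalation) and Section 3.1.2.1.1 agree on the principle. A first delayed DLT, meaning any DLT at 4 to 6 weeks, lengthens the DLT period to 42 days for all ongoing and later dose-escalation patients. Without one, the period stays at 28 days.

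**Laboratory exemption.** The Synopsis then states: "AST, CK, or LDH laboratory abnormalities without clinical sequelae are not considered a delayed DLT (see Section 3.1.2.1.1"). Section 3.1.2.1.1 has no separate exemption in its delayed-DLT paragraph. Its general exemption is bounded. It applies "In the absence of clinical symptoms and other accompanying changes in bilirubin or ALT", covers AST/ALT above 12 and up to 20 xULN and CK and/or LDH above 15 and up to 20 xULN, and requires the elevation to last less than 7 days.

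**Window wording.** Section 3.1.2.1.1 defines a DLT as a drug-related event of Grade 3 or higher "occurring during the first 28-days", with listed exclusions. The Synopsis says: "The DLT evaluation interval begins on the first day of treatment and continues for 28 days". Section 3.1.2.1 repeats this, and the escalation rules count DLTs over that interval.

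**Evaluability and replacement.** A patient is evaluable with two doses in 28 days, or after stopping early for a drug-related adverse event. The Synopsis has "Patients who receive at least 2 doses of study drug during the 28-day evaluation interval" and Section 3.1.2.1 has "Patients that receive at least 2 doses of study drug during the 28-day evaluation interval". Section 3.1.2.1 replaces a patient who misses the two doses and also misses the safety assessments in the DLT period, for reasons other than drug-related events.

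Section 1.8.1, Appendices F to H and the escalation algorithm table are not visible in the public documents.

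**The concern.** The trigger decides how long every remaining escalation patient is watched before a dose decision. Two sections state it differently, and one cites the other.

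Laboratory events are the kind that has driven this escalation. Section 3.1.2.1 reports that both DLTs in 1aM2 (6 mg/kg) were laboratory abnormalities, and that the laboratory cut-offs were raised after two further DLTs in 1aM3 (4 mg/kg). The named escalation still to come is at 6 mg/kg: 1aM2 re-opened, then possibly 1aC4. DLT incidence is a Phase 1a primary endpoint (Section 7.3.1.1). Neither Protocol Section 7.2 nor SAP Section 7.2 defines a DLT-evaluable population, so the wording in the design sections also settles who enters the denominator.

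If the period is extended, a patient can count as DLT-free without having been followed through the added two weeks. That is the direction of error that favours escalation.

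**Working it through.** The plan gives no figure on this point to reproduce. The check sets the rules side by side and works out the days.

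**1. Trigger.** Take a drug-related, symptom-free AST or CK of 25 xULN in week 5, of Grade 3 or higher, with no accompanying bilirubin or ALT change.

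| | Synopsis | Section 3.1.2.1.1 |
|---|---|---|
| Upper limit | none stated | 20 xULN |
| Duration limit | none stated | under 7 days |
| Analytes | AST, CK, LDH | AST, ALT, CK, LDH |
| 25 xULN exempt? | yes | no (25 > 20) |
| Delayed DLT? | no | yes |
| DLT period | 28 days | 42 days |

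The value lies above the 20 xULN ceiling, so the result does not depend on how lower elevations are handled in the appendices that are not visible. It is also a level at which Section 4.3.5 calls for stopping treatment: it lists drug-related AST or ALT above 20 xULN as a reason to discontinue, and it spares Grade 4 CK only up to 20 xULN.

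**2. Window wording.** Read literally, a DLT must fall in the first 28 days, so a DLT at 4 to 6 weeks could not exist and the extension could never start. The extension clause shows that this is not meant. The definition and the evaluation interval were simply not rewritten to match it.

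**3. Evaluability after an extension to 42 days.** Take a patient dosed on days 1 and 15 who leaves the study treatment after day 28.

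- Two doses within 28 days: evaluable under the Synopsis and Section 3.1.2.1.
- Replacement needs both missed doses and missed safety assessments. Both doses were given, so the patient is not replaced.
- Section 3.1.3 places the first End-of-Treatment visit 28 (±7) days after the last dose: 15 + 28 = day 43, so days 36 to 50.
- At the earliest visit, 42 − 36 = 6 days of the period are still to come.
- Adverse event reporting runs to 100 days after the last dose but ends if new anti-cancer therapy starts, which may be before day 42.

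Nothing in the evaluability rule requires follow-up to day 42.

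**4. Visits already scheduled.** On 14-day cycles, safety laboratories fall on days 1, 8, 15, 29 and 43. The day-43 draw (Cycle 4 Day 1) may be taken up to 72 hours before dosing, so from day 40. For a last dose on day 29, the first End-of-Treatment visit is day 29 + 28 = 57, so days 50 to 64.

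**5. Reach.** Section 7.1 expects 3 to 9 patients per escalation cohort.

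**The case against.** The strongest reply on the trigger is that the Synopsis sentence is a summary. It sends the reader to Section 3.1.2.1.1, so the limits there could be taken as imported. Alternatively, a wider exemption for late laboratory events may be deliberate, since the cut-offs were raised on purpose. Either may be true, but the sentence does not say that it imports limits, and Section 3.1.2.1.1 contains no wider late exemption. On either reading one of the two places needs correcting. The sections that are not visible may hold further detail, but they do not remove the conflict between two that are.

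A reader might infer that DLT counting stays at 28 days after an extension, so that a DLT on day 35 in 1 of 3 patients would be scored 0/3 and the dose escalated. The documents do not support that. Both the Synopsis and Section 3.1.2.1.1 lengthen the DLT period to 42 days and keep 28 days only if no delayed DLT occurs. Under that intent the score is 1/3 and three patients are added. What stands is that the definition and the interval were not reconciled with the clause.

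A reader might also infer that a patient who starts new therapy on day 29 goes unobserved for the last 14 of the 42 days. That is too strong. Section 3.1.3 calls all patients back 28 (±7) days after the last dose, and Sections 5.2.1.9 and 5.2.2.11 include safety laboratories at that visit. Observation is reduced, not absent.

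Oversight limits the effect. Investigators and the Medical Monitor determine DLTs, "a safety teleconference will be held wherein the Investigators and Sponsor will review patient data" before each new dose level, and the Cohort Review Committee (Section 8) also reviews the data. The patient in the 25 xULN example is covered by the Section 4.3.5 discontinuation rule under both readings. Phase 1b already has a stated cabiralizumab dose of 4 mg/kg, although Section 3.1.2.5 allows it to change on later Phase 1a data. These safeguards lower the risk, but they do not say which rule sets the window.

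**Conclusion.** The point holds, with moderate confidence, as two defects of wording that affect dose decisions.

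First, the Synopsis and Section 3.1.2.1.1 give different DLT periods, 28 and 42 days, for the same late laboratory event. This assumes that the event is drug-related and of DLT grade, and that nothing in Section 1.8.1, Appendices F to H or the algorithm table settles it.

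Second, the 28-day wording in the DLT definition and evaluation interval was not aligned with the extension. In consequence, a patient with two doses in 28 days who leaves after day 28 counts as evaluable and is not replaced, although follow-up to day 42 is not required. In the worked case the next visit may come as early as day 36, and adverse event reporting may already have ended.

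The consequence is limited to the remaining escalation cohorts. The documents give no rate of late events, so no probability of a changed decision is claimed.

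**What to change.** 1. State one laboratory exemption in Section 3.1.2.1.1 that covers both DLTs and delayed DLTs, and make the Synopsis refer to it without restating it. If a wider exemption for late events is wanted, write it there with explicit xULN and duration limits. The level is the sponsor's choice; 20 xULN would match Section 4.3.5.
2. In the DLT definition and the evaluation interval (Synopsis, Sections 3.1.2.1 and 3.1.2.1.1), replace the fixed 28 days with the applicable DLT period: 28 days from first dose, or 42 after a delayed DLT. Define a delayed DLT as an event that meets the same criteria after day 28 and up to day 42.
3. Keep the requirement of two doses in the first 28 days. Add that a patient without a DLT must be followed for safety to the end of the applicable period to be evaluable, and replace those who are not. Patients with a DLT, or who discontinue for a drug-related adverse event, remain evaluable.

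Existing visits can serve as the end-of-period check where possible: the Cycle 4 Day 1 pre-dose laboratory, or, for a last dose on day 15, the 28-day End-of-Treatment visit placed on or after day 42. A patient who stops after the day-29 dose would need one added laboratory near day 42, because the scheduled visit falls on days 50 to 64.

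The cost is amendment wording, that occasional extra sample, and slightly more window extensions and patient replacements.

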## Study Design (cont.)

Phase 1a: 3-Week Dosing Regimen	An alternative dosing regimen cohort (1aD) with 10 patients has been added to characterize the PK and safety of cabiralizumab in combination with nivolumab when administered at a 3-week dosing schedule. In this cohort, 4 mg/kg cabiralizumab in combination with 3 mg/kg nivolumab will be administered intravenously every three weeks until disease progression, unacceptable toxicity, or other reason for treatment discontinuation. Patients who enter this cohort will follow eligibility criteria for Phase 1a. Patients will not be evaluated for DLT as the dose frequency is less than Cohort 1aC3 which has cleared the DLT window at the time of this amendment.
Phase 1a: Exploration Cohort	Based on emerging clinical and translational data, up to 40 patients will be included in Phase 1aE to further explore safety, PK, and PD at alternative dose levels or dosing schedules which have already successfully cleared their respective DLT periods. In each cohort, cabiralizumab either as monotherapy or in combination with nivolumab will be administered until disease progression, unacceptable toxicity, or other reason for treatment discontinuation. Patients who enter Phase 1aE will follow eligibility criteria for Phase 1a.
Phase 1b: Dose Expansion	Seven cohorts consisting of approximately 30 patients each in specific tumor types will characterize the safety and evaluate the efficacy at the RD of cabiralizumab in combination with nivolumab. In each cohort, 4 mg/kg cabiralizumab in combination with 3 mg/kg nivolumab will be administered intravenously every 2 weeks until disease progression, unacceptable toxicity, or other reason for treatment discontinuation.

### **Notable Aspects of Study Conduct:**

#### **Study History**

- Cohort 1aM1 (2 mg/kg cabiralizumab monotherapy) was enrolled first, followed by enrollment of a cohort of 3 new patients in the 1 mg/kg cabiralizumab and nivolumab combination cohort (1aC1).
- Cohort 1aM2 (6 mg/kg cabiralizumab monotherapy) was opened after the DLT period cleared in the 2 mg/kg cabiralizumab monotherapy cohort (1aM1).
- Cohort 1aM3 (4 mg/kg cabiralizumab monotherapy) was opened after DLTs were observed in Cohort 1aM2.
- Cohort 1aM2 (6 mg/kg cabiralizumab monotherapy) was re-opened after the DLT period cleared in the 1aM3 (4 mg/kg cabiralizumab monotherapy) cohort (See Section 1.4 for the rationale for re-opening Cohort 1aM2)

## Study Design (cont.)

### Phase 1b: Dose Expansion (cont.)

- Cohort 1aC2 (2 mg/kg cabiralizumab and nivolumab combination) was opened after the DLT period cleared in the 1 mg/kg cabiralizumab and nivolumab combination cohort and 2 mg/kg cabiralizumab monotherapy cohorts (1aC1 and 1aM1, respectively).
- Cohort 1aC3 (4 mg/kg cabiralizumab and nivolumab combination) was opened after the DLT period cleared in the 1 mg/kg and 2 mg/kg cabiralizumab and nivolumab combination cohorts (1aC1 and 1aC2 respectively) and in the respective monotherapy cohorts.

### Study Plan

- At least 3 patients will be enrolled into each dose escalation cohort.
- Upon completion of the DLT period, approximately 40 additional patients may be enrolled in Phase 1aE to further characterize safety, PK, and PD.
- Alternative dose levels of cabiralizumab may be tested based on safety, PK and biomarker data.
- Patients in the combination cohorts can be treated beyond disease progression in accordance with protocol specific guidelines (see Section 4.3.8).
- Tumor biopsies will be performed in at least 10 patients in each Phase 1b dose expansion cohort (optional for cohort 1b7 GBM) before treatment, at 1 month post-treatment
- Skin biopsies will be performed in all Phase 1a patients before treatment, at 1 month post-treatment.
- Post-disease response and/or progression tumor biopsy and skin biopsy will be optional for all patients.

